## **2.0 Rationale and Specific Aims**

The goal of this study is to assess whether using PTeye – a NIRAF detection modality – can improve patient outcomes and reduce healthcare associated costs after parathyroid surgeries. The specific aims of this study is to determine if PTeye is beneficial or not for (i) intraoperative identification of parathyroid tissues, (ii) improving efficiency of parathyroid surgeries, and (iii) minimizing risk of postsurgical complications.

By being able to quickly and definitively locate parathyroid glands while in the operating room, the duration of surgical procedure could be further reduced. In addition, the number of frozen section biopsy and associated costs can be minimized. Furthermore, repeat surgeries as a result of missing a diseased parathyroid gland at the time of the initial parathyroidectomy for hyperparathyroidism could potentially be avoided.

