## 6.0 Study Procedures

For patients assigned to the study arm, the surgeon will use the PTeye as an intraoperative tool to identify if a suspect tissue is a parathyroid or not, during the parathyroid surgery. The surgeon will first take 5 baseline NIRAF measurements on the thyroid gland (or neck muscle, if thyroid is absent) using the disposable sterile fiber probe that is connected to the PTeye console (see Figure 1), as per device functionality requirements. The subsequent step would involve touching the target tissue in the neck with the fiber optic probe, following which the PTeye will indicate to the surgeon if the tissue is parathyroid or not. Parameters which are displayed on the PTeye console – Baseline values, Detection Intensity, Parathyroid Detection Ratio – will be recorded for each patient enrolled in the study arm. PTeye indicates that a tissue is parathyroid if it displays the 'Parathyroid Detection Ratio' is greater than 1.2. The rest of the surgical procedure will follow according to standard protocol.

For patients assigned to the control arm, the surgeon will not use the PTeye and will proceed with the parathyroid surgery as usual, while relying solely on her/his surgical experience in identifying the parathyroid glands during the operations.

**Figure 1.** A commercial fiber probe-based system (PTeye, AiBiomed) for detecting near infrared autofluorescence (NIRAF) utilized for intraoperative parathyroid gland identification. PTeye consists of 1) the console that has a display and indicates to the surgeon if a tissue is parathyroid or not, 2) a detachable fiber optic probe, and 3) a foot-pedal which is activated by the surgeon for tissue NIRAF measurements.

De-identified information regarding (i) patient demographics, (ii) duration of surgery, (iii) number of frozen section analysis performed, (iv) frozen section and permanent histology reports of all excised tissues, (v) blood calcium levels (before surgery, 5-14 days after

surgery and 6 months after surgery), (vi) parathyroid hormone (PTH) levels (5-14 days after surgery and 6 months after surgery) and (vii) postsurgical complications, if any and history of ER visits or hospitalization or repeat surgeries due to high calcium, will be compiled for all enrolled patients. These parameters would then be compared between the study arm and the control arm to truly gauge the impact or value of a device like PTeye for parathyroid surgeries.

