## **10.0 Statistical Considerations**

Benmiloud *et al.* studied the impact of NIRAF-based identification of parathyroid glands which comprised of a group of 93 patients where NIRAF was used by a surgeon for parathyroid identification and a control group of 153 patients where NIRAF was not used (19). Their study reported that mean parathyroid glands identified by surgeon with NIRAF imaging was significantly higher at  $3.1 \pm 0.9$ , while that of same surgeon without NIRAF imaging was  $2.6 \pm 0.1$  ( $p=0.0001$ ). Based on this data (mean difference: 0.5 and standard deviation: 1.0), it was determined that in order to observe a statistically significant difference (i.e. for an expected mean difference: 0.7 and expected standard deviation: 1.0), 33 patients would be required per group (for a 95% powered study). Since this study may involve patient follow-up for data up to 6 months after surgery, we will thus assume an approximate data attrition rate of 20%, thus requiring a recruitment of 40 patients per group. In order to detect a difference among individual surgeons, this will require recruitment of 40 patients per arm, per surgeon. Therefore, a total of 160 patients (study and control arm) should be recruited for this study at this study site.

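### The 33 (raised to 40) patients per group repeated for each surgeon give about 80% power (79-87%), not the stated 95%, and a surgeon difference in PTeye benefit is not sized

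*Combined protocol and SAP*

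**What the plan says.** Section 10.0 (Statistical Considerations) cites an earlier NIRAF study and summarises it as "Based on this data (mean difference: 0.5 and standard deviation: 1.0". The trial itself is sized "for an expected mean difference: 0.7 and expected standard deviation: 1.0", from which the plan concludes that "33 patients would be required per group (for a 95% powered study". An allowance of 20% for data attrition raises this to 40 per group, or 80 patients.

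The plan then adds: "In order to detect a difference among individual surgeons, this will require recruitment of 40 patients per arm, per surgeon". It concludes: "Therefore, a total of 160 patients (study and control arm) should be recruited for this study at this study site". The surgeon sentence is the only reason given for 160 rather than 80. Section 10.0 gives no alpha, no sidedness, no number of surgeons, no expected difference between surgeons and no surgeon-level test.

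The first aim in section 2.0 is to "determine if PTeye is beneficial or not for (i) intraoperative identification of parathyroid tissues". Section 6.0 lists the data to be compiled, including "iii) number of frozen section analysis performed, (iv) frozen section and permanent histology reports of all excised tissues", and says "These parameters would then be compared between the study arm and the control arm". The number of glands identified, on which the trial is sized, is not named in that list.

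**The concern.** A figure for a single two-arm comparison is reused for each surgeon with its 95% label attached. Two things can go wrong.

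- If 33 per group does not give 95% power for the stated inputs, neither does the same size within each surgeon.
- Detecting a difference among surgeons can mean three things: (a) the PTeye effect within each surgeon, which is the natural reading; (b) a difference between surgeons in PTeye benefit, which is an arm-by-surgeon interaction; or (c) a difference in surgeons' average gland counts. These need different numbers of patients, and the plan does not say which it means.

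At stake is the stated justification for half the patients, and how a null result for one surgeon will be read. Someone who trusts the 95% label will think a true 0.7-gland effect would be missed only 5% of the time.

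**Working it through.** **Inputs from section 10.0.** Difference 0.7; SD 1.0; 33 per group; 40 recruited per arm per surgeon; 20% attrition; 160 in total.

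**Assumptions.** Two-sided 5%, with one-sided 5% as a check. Two surgeons, inferred from 160/(2 × 40) = 2. Evaluable patients per arm per surgeon (n): 40 with no loss, 40 × 0.8 = 32 with 20% loss.

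**Reproducing the plan's 33.** By the normal approximation, n per group = 2(z₁₋α/₂ + z₁₋β)² SD²/δ²:

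- 80% power: 2(1.960 + 0.842)²/0.49 = 32.04, so 33.
- 95% power: 2(1.960 + 1.645)²/0.49 = 53.04, so 54. The t-test gives 54.02, so 55.

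The plan's 33 is therefore the 80% answer. At one-sided 5%, 95% power needs 45. To reach 95% with 33 per group (two-sided 5% unless alpha is the item changed), one input would have to change: a difference of 0.90, an SD of 0.78, or a two-sided alpha of about 24%.

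**From 33 to 160.** 33 × 1.2 = 39.6, so 40; 40 × 2 arms × 2 surgeons = 160.

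**Power by reading of the surgeon sentence** (noncentral t, SD 1.0, two-sided 5%):

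| Contrast | SE | df | Difference | n = 32 | n = 33 | n = 40 |
|---|---|---|---|---|---|---|
| (a) PTeye effect within one surgeon | √(2/n) | 2n − 2 | 0.7 | 78.7% | 80.0% | 87.1% |
| (a) same | √(2/n) | 2n − 2 | 0.5 | 50.4% | 51.6% | 59.8% |
| (b) arm-by-surgeon interaction | √(4/n) | 4n − 4 | 0.7 | 50.2% | 51.4% | 59.5% |
| (b) same | √(4/n) | 4n − 4 | 0.35 | 16.6% | 17.0% | 19.6% |
| Overall PTeye v control, adjusted for surgeon | √(1/n) | 4n − 3 | 0.7 | 97.6% | 97.9% | 99.3% |
| Overall, same | √(1/n) | 4n − 3 | 0.5 | 80.1% | 81.4% | 88.2% |

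- One-sided 5%, difference 0.7: (a) 87.0%, 87.9% and 92.8%; (b) 62.7%, 63.9% and 71.2%. None reaches 95%.
- The interaction is the difference of two independent within-surgeon effects, so its variance is 2/n + 2/n = 4/n, twice that in (a). The documents give no interaction size; 0.7 (as large as the whole expected device effect) and 0.35 (half of it) are illustrations.
- Reading (c) has the same SE as the overall comparison, so 98-99% power for 0.7. It does not address the PTeye aims in section 2.0.
- 95% CI half-widths for n from 40 down to 32: 0.45-0.50 glands for (a), 0.62-0.70 for (b).
- The overall comparison reaches 95% power for 0.7 with 28 evaluable per arm per surgeon: 4 × 28 = 112, and 112/0.8 = 140 recruited. The planned 160 covers this.

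**The case against.** The strongest objection is that the 95% label may not be the faulty item. Section 10.0 also reports 3.1 ± 0.9 in 93 patients and 2.6 ± 0.1 in 153. Pooling these gives an SD of √[(92 × 0.81 + 152 × 0.01)/244] = 0.558. With a difference of 0.5, the 95% formula gives 2(3.605)² × 0.3116/0.25 = 32.4, so 33. Hence 33 at 95% can be reached from other figures in the same paragraph. This remains possible, and the sponsor should check where 33 came from. It does not rescue the sentence: the plan names SD 1.0 twice and 0.7 as its design difference, and with those inputs 33 gives 80%. The 95% might also have been meant as a confidence level, but the text says powered.

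Second, the attrition is tied to 6-month follow-up, while glands identified are known at surgery. If nothing is lost for that count, within-surgeon power is 87%, the top of the range. This is fair, but the plan itself applies the 20% to this sample size, and 87% is still short of 95%.

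Third, the plan never promises an interaction test, and the sizes used for it above are not the plan's. That is true, and the interaction figures are conditional for that reason. The wording about a difference among surgeons nevertheless invites that reading, and nothing in section 10.0 rules it out.

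Finally, the overall comparison is well powered. That stands, and it limits the consequence to the stated power and the rationale for 160.

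**Conclusion.** The concern holds. For the plan's own 0.7 and 1.0, the stated 95% is wrong at either conventional sidedness: 33 per group gives 80% two-sided or 88% one-sided.

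On the natural reading, the chance of missing a true 0.7-gland effect with one surgeon is 13-21%, not the implied 5%. On the interaction reading the contrast is not sized, and the chance of missing a 0.7-gland difference between surgeons in benefit would be 40-50%.

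These figures rest on two-sided 5%, SD 1.0 and 32-40 evaluable per arm per surgeon; those for the interaction and the overall comparison also rest on two surgeons. The main PTeye versus control comparison exceeds the plan's 95% target for 0.7 at 160 patients. This should be fixed, but it does not threaten the trial's main result.

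**What to change.** Keep 160 and change section 10.0 as follows.

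1. Correct the power statement: 33 evaluable patients per group give about 80% power for a difference of 0.7 with SD 1.0 at two-sided 5%. State alpha and sidedness. If 33 was in fact derived from other inputs, give those instead and recompute.
2. Replace the surgeon sentence with what 160 delivers. For example: *With two surgeons and 40 patients per arm per surgeon (64-80 evaluable per arm overall), the comparison of glands identified, PTeye v control, adjusted for surgeon, has 98-99% power for a difference of 0.7 and 80-88% for 0.5. The PTeye effect within one surgeon has 79-87% power for 0.7.*
3. State that within-surgeon effects and the arm-by-surgeon interaction are secondary and are reported as estimates with 95% CIs (expected half-widths about 0.45-0.50 and 0.62-0.70 glands). Drop the claim that 40 per arm per surgeon is enough to detect a surgeon difference in PTeye benefit. If average counts between surgeons were meant, say so.
4. As a smaller matter, name the gland count among the parameters compared in section 6.0.

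The cost is wording, one model term for surgeon and a less favourable stated power per surgeon. No extra patients are needed. If the sponsor does want 95% power within each surgeon, the price is 55 evaluable per arm per surgeon: 55/0.8 = 68.75, so 69 recruited, and 4 × 69 = 276 in total for two surgeons.

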## **11.0 Privacy/Confidentiality Issues**

All study staff are required to complete the CITI Protection of Human Subjects Training Program. All data pertaining to this study will be stored in the HIPPA compliant REDcap data management program. Access to study data will be limited to the investigators listed on the study only. Only indirect identifiers such as medical record number (MRN) will be used. Participants' information, including his or her name and medical record number, will be available only to the PI and key study personnel. It will be stored in a password-protected computer and a locked file cabinet in the study coordinator's office where we also will store the consent forms. All records will only be available to the PI and key study personnel. All information potentially identifying the participant will not be included in the data analysis or reporting of results therein.

## **12.0 Follow-up and Record Retention**

The duration of the study is expected to be approximately two years and will depend on patient availability. The data acquired from this study will be preserved indefinitely, as it may influence the future development of the entire research project. However, the data will not be accessible to anyone other than the participants of this study. All original paper records, record sheets, preoperative and postoperative lab investigations, drug/medication history, post-surgical medical history, histopathological diagnoses of the investigated tissue samples, will be collectively retained by the PI or Key Study Personnel. The data of this study will be stored in a password protected computer, and only users with permission from the PI can access the data base.

